3.1 Overview

On admission to the CRC, (1) a GW biographer will be placed, (2) a CGMS inserted, and (3) an intravenous catheter inserted for the gold standard glucose measurements. Subjects will be in the CRC for approximately 26 hours.

The inpatient procedures are summarized below and detailed in subsequent sections.

The study will consist of the following:

- 1) Gold standard blood glucose measurements will be hourly during the day and every half hour overnight.
- 2) The accuracy of the CGMS sensor will be assessed for approximately 24 hours. Simultaneous use of a second CGMS sensor during the inpatient stay will be optional.
- 3) The accuracy of the GW biographer will be assessed over approximately 24 hours of use, with a minimum of a 2-hour period of time where the use of two biographers will overlap.

3.2 Sensor Management and Procedures

3.2.1 GlucoWatch Biographer

The second generation device will be used for these studies. Subjects will wear the biographer on the forearm or upper arm. The time of placement and the placement site of each biographer will be recorded (right or left arm, inner or outer arm, forearm or upper arm). An assessment will be made of the skin in the area of sensor placement. The biographer alarm settings will be set to be 40 mg/dl (low) and 400 mg/dl (high).

The first biographer (GWB#1) will be placed at the time of admission and calibrated two hours later. The second biographer (GWB#2) will be placed after GWB#1 is calibrated and no later than 9 hours after GWB#1 is calibrated, with its calibration completed two hours later. Assuming that GWB#1 does not prematurely shut off without being replaced, there will be at least two hours of overlap between the two biographers. If the timing of placement of GWB#2 is such that it will be removed prior to the end of the 24 hours of gold standard measurements, then GWB#1 will be used a second time with a second sensor (placed coincidentally with removal of the first GWB#1 sensor and calibrated two hours later). If GWB#2 sensor is removed 4 or more hours prior to the last 24-hour gold standard measurement, then a second GWB#2 sensor can be placed at investigator discretion. A sensor may be removed and replaced with a new sensor prior to the end of 15 hours if necessary to avoid having to place a new sensor overnight while the subject will be asleep.

Calibration glucose values will be obtained with the study HGM using venous blood obtained at the time of a gold standard blood draw. After the initial calibration, additional calibrations will be performed when the required CGMS calibrations are performed.

Prior to hospital discharge, a skin assessment will be made by two observers for all areas where a biographer was worn. Both erythema and edema will be scored on a 0 to 4 scale (as described on the case report form and in the Procedures Manual). If the sum of the erythema score and the edema score is 6 or greater, an Adverse Event Form will be completed.

3.2.2 Continuous Glucose Monitoring System

The CGMS sensor will be inserted in the abdomen or upper buttocks in an area of normal appearing skin. The site and time of insertion will be recorded. The area where the sensor will be inserted may be numbed with Elamax or EMLA cream for at least 15 minutes prior to insertion.

Calibration values will be obtained with the study HGM using venous blood obtained at the time of a gold standard blood draw. After the initial calibration, glucose measurements will be entered before each meal and before bed.

Simultaneous use of a second CGMS sensor will be optional. If the investigator believes that the child can successfully use two CGMS sensors and the subject and parent agree, a second sensor will be inserted in an area of normal appearing skin, similar to the procedure described above for the first sensor. There is no increased risk to the subject of having two sensors.

Prior to hospital discharge, the CGMS will be removed and the insertion site will be assessed for induration (measured in millimeters), and erythema (measured in millimeters).

3.2.3 Sensor Failure and Related Issues

If a GlucoWatch biographer sensor fails with fewer than 4 hours of gold standard measurements remaining, it will not be replaced. The schedule for subsequent sensor placement will not be altered.

If a CGMS should fail (ISIG < 10 with glucose >120) or there are frequent interrupt alarms, or the sensor fails to accept a calibration glucose value, then a new CGMS sensor will be inserted and the failing sensor will be removed. If the sensor is removed because of frequent interrupt alarms, a new cable will be used. If a sensor fails within 3 hours of the completion of the inpatient study, it will not be replaced.

A subject who is unable to use the sensors will be withdrawn from the study and will not be counted towards the recruitment goal when he or she is unable to successfully use the CGMS for 12 hours and one biographer for 12 hours as an inpatient. If the subject has used at least one sensor successfully as an inpatient for 12 hours, the inpatient phase will be completed as long as one sensor is still being used.

3.3 Gold Standard Glucose Measurements

An intravenous catheter will be inserted in an arm vein. The area where the catheter will be inserted may be numbed with Elamax or EMLA cream for at least 15 minutes prior to catheter insertion.

The gold standard measurements will be timed to be on the hour and, when specified in the protocol to be performed overnight, on the half-hour. The first hourly measurement will be made at the first hour point that is at least one hour following insertion of the CGMS. Half-hourly measurements will be made from 9:00 p.m. to 7:00 a.m. If the catheter stops functioning, it will be replaced if there are any protocol-specified gold standard measurements still to be made.

The clinical centers either will use reinfusion of blood or will discard blood with each blood draw, depending on the standard practice at each center's CRC. The blood draws will be performed by the method in standard use at the CRC. The blood samples will be sent to a central lab.

3.3.1 Volume of Blood Draws

The total blood volume withdrawn during the study for the hourly blood draws for 24 hours and the half-hour blood draws overnight for 10 hours will be 10.2 ml with reinfusion (assuming a blood volume of 0.3 ml per blood draw) and 44.2 ml with discard (assuming a blood volume of 1.3 per blood draw).

Additional blood draws may be needed for the GlucoWatch biographer calibrations. One to three duplicate blood samples will be drawn for quality control purposes from each subject. For four calibration blood draws and three quality control blood draws, the blood volume will be 2.1 ml at reinfusion centers and 9.1 ml at discard centers.

The minimum weight requirement of 16 kg for subject eligibility assures that the maximum blood volume in the blood draws (53.3 ml at discard centers) will not exceed 5% of a subject's blood volume (calculated by multiplying the subject's weight in kilograms by 70 [70cc / kg blood volume] and then multiplying by .05).

3.4 Daily Activities

Subjects will be permitted to perform their usual indoor activities during the hospitalization.

3.5 Diet

A regular diet for age will be prescribed.

3.6 Hospital Discharge

Prior to discharge, all sensors will be removed and a CRC nurse and a study nurse or investigator will independently assess the skin in the area of each GW biographer wear and each CGMS insertion (see sections 3.2.1 and 3.2.2).

CHAPTER 4 POST-DISCHARGE FOLLOW UP

4.1 Follow-up Visit

All subjects will return 3 to 5 days after discharge from the CRC for an inspection of the CGMS insertion site and the biographer wear sites for any redness, swelling or blistering.

4.2 Additional Follow-up for Sensor Skin Effects

If at the day 3-5 visit, there is any redness, swelling, or blistering, the subject will be contacted by phone by the study investigator or his/her designee 10 to 14 days after discharge. If there are persistent skin changes, the subject will be asked to return for a physical assessment.

A subject with persistent active skin changes will be called weekly until the changes resolve.

CHAPTER 5 ADVERSE EVENTS

All adverse events occurring during the course of the study will be recorded on the appropriate case report form(s). Skin irritation from sensor wear will be recorded in a specific section of the case report forms. Other adverse events will be reported on an adverse event case report form.

5.1 Definitions

An *Adverse Event* (AE) is defined as any untoward medical occurrence in a research subject treated with a medical device during a clinical trial or post-study follow-up period, regardless of causality assessment. This includes adverse clinical or laboratory findings, intercurrent illness, or an exacerbation or progression of a disease/condition present at baseline. The event(s) will be reported with reference to: time and date of event, relationship to the device, severity and final outcome. For this study all adverse events, regardless of causality and relationship to sensor use or study procedures, will be reported during the period of time of sensor use. Following the completion of sensor use and all study procedures, only adverse events with a possible or greater relationship to sensor use or study procedures will be reported.

An adverse event is considered a *Serious Adverse Event* (SAE) when it meets one or more of the following criteria: (1) death, (2) life-threatening, (3) required or prolonged hospitalization, (4) permanent disability, or (8) required intervention to prevent permanent impairment/damage.

An *Unanticipated Adverse Device Event* is defined as an adverse event caused by, or associated with, a device, if that effect or problem was not previously identified in nature, severity, or degree of incidence.

The relationship of any adverse event to the device or any other aspect of study participation will be assessed and graded by a study investigator on a four-point scale: (1) not related, (2) possible, (3) probable, and (4) definite. The intensity of adverse events will be rated on a three-point scale: (1) mild, (2) moderate, or (3) severe. It is emphasized that the term severe is a measure of intensity: thus a severe adverse event is not necessarily serious. For example, itching for several days may be rated as severe, but may not be clinically serious.

5.2 Skin Irritation

Skin irritation is a possible effect of the biographer. For all subjects, skin irritation will be formally assessed at the time of CRC discharge (see section 3.2.1 and 3.2.2). A biographer irritation score of 6 is considered an Adverse Event and will be recorded on an Adverse Event Form in addition to being recorded on the skin assessment case report form. Skin changes in the area of the insertion of the CGMS catheter (induration and erythema) also will be assessed.

5.3 Reporting Requirements for Serious and/or Unexpected Adverse Events

Any serious or unexpected adverse event occurring during or after completion of the study, irrespective of the treatment received by the patient, will be reported to the Coordinating Center within one working day of occurrence. A written report on such an event will be sent to the Coordinating Center within five days of occurrence, stating a description of the reaction, any required intervention and the outcome. Each principal investigator is responsible for informing his/her IRB of serious study-related adverse events and abiding by any other reporting requirements specific to their IRB. Contact information for the Coordinating Center is located in the front of the protocol as well as in the Study Directory.

5.4 Data and Safety Monitoring Board

An independent Data and Safety Monitoring Board will approve the protocol prior to its initiation and will be informed of any serious adverse events that occur during the study.

5.5 Risks And Discomforts

5.5.1 GlucoWatch Biographer

Previous studies done at Cygnus with earlier versions of the biographer have provided evidence that the application of up to 0.3 mA/cm² for up to 2 hours is safe. The biographer is designed to prevent current surges and has appropriate safety features to prevent high current or voltage levels. The device can apply a maximum of 17 volts. As a safety mechanism, the biographer will shut off automatically once 16 volts have been applied. Iontophoresis can cause a mild tingling sensation. If the subject feels significant discomfort, he/she will be able to turn off the current.

The most common reaction is skin irritation. The irritation will usually manifest itself as erythema and edema at the iontophoresis site. Irritation from iontophoretic current may cause dryness, flaking or itching at the site for several days after treatment. Slight skin discoloration may be present after treatment, which gradually fades over several days. Severe irritation (equivalent to a chemical burn at or near the application area, generally 1-3 mm in diameter) is a potential risk. The severe irritation regions with necrosis, resembling small blackheads, become evident only upon device removal. A small percentage of severe irritation events have occurred using previous versions of the biographer. The severe irritation events that occurred caused little or no discomfort to the subject. All severe irritation events caused by previous biographer versions have been addressed with the subsequent design changes. No severe irritation events have occurred using the current biographer version and are not expected to occur with the biographer version(s) being used in this study. A thermal burn is not a potential risk, as the maximum possible current the biographer can deliver is 0.4 mA.

There may be skin irritation from the two, small skin conductivity measurement probes on the underside of the biographer. The current expected to be delivered by the probes is more than 300 times lower than the iontophoretic current, and the surface area contacted by is approximately 19 times smaller than the area subject to iontophoretic current. In addition, the current for the probes will only be activated for 30 seconds at a time, up to once per minute. If for some reason the conductivity probes were to malfunction, the maximum current they could deliver would be approximately 20 times less than the iontophoretic current. With the application of current at the measurement probes, severe irritation is also a potential risk. However, no severe irritation events with the current biographer version have occurred.

5.5.2 CGMS Sensor

Subjects using the CGMS will be at low risk for developing a local skin infection at the site of the sensor needle placement.

CHAPTER 6 MISCELLANEOUS ISSUES

6.1 Benefits

There will be no a direct benefit to the subject from participating in this study. The subject's participation in this study is an important contribution to the development of a better understanding of normal glucose metabolism in children.

6.2 Subject/Parent Reimbursement

The subjects and their families will be paid \$100 for the CRC admission as compensation for their travel expenses and potential time lost from work for the hospitalization phase of the study. They will also receive \$25 for each outpatient visit. If the optional second CGMS sensor is inserted, an additional \$25 will be paid.

6.3 Subject Withdrawal

Participation in the study is voluntary, and a subject may withdraw at any time.

The investigator may withdraw a subject who is not complying with the protocol.

A subject who is enrolled but at the time of CRC admission is found to have an abnormal HbA1c or hematocrit will be withdrawn. An enrolled subject who at the time of CRC admission reports having used a systemic medication (prescription or nonprescription) in the prior 7 days will either be rescheduled or withdrawn.

A subject who is unable to use the sensors will be withdrawn and will not be counted towards the recruitment goal when he or she is unable to successfully use at least one CGMS and one biographer for 12 hours as an inpatient.

Subjects who withdraw or are withdrawn from the study without completing at least 12 hours of sensor use will be replaced if the full cohort has not yet been recruited at the time the subject is withdrawn from the study.

Subjects who are admitted to the CRC and have at least one gold standard blood measurement will receive payment for the inpatient stay even if withdrawn prior to completion of the study.

6.4 Confidentiality

Individual patient medical information obtained as a result of this study is considered confidential and disclosure to third parties other than those noted below is prohibited. Such medical information may be given to the patient's personal physician or to other appropriate medical personnel responsible for the patient's welfare. Data generated as a result of this study are to be available for inspection upon request by the Coordinating Center, the NIH, and auditors of regulatory agencies as required by law.

Data will be transmitted to the study's Coordinating Center for storage and analysis. The names and any other identifying information of the subjects and parents will not be part of the information that is sent to the Jaeb Center. The Coordinating Center maintains secure patient data files (both physical files and the computerized database). Data are stored such that no direct links exist between the patient's data and information that would identify the patient.

CHAPTER 7 STATISTICAL CONSIDERATIONS

7.1 Sample Size

The sample size of 20 normal subjects was selected to provide preliminary data on the accuracy of the sensors in normal children. Based on outpatient use of the CGMS, it is expected that at least several of the 20 children will demonstrate prolonged periods of low blood glucose values using the CGMS. Thus, a sample size of 20 should provide the opportunity of determining whether or not these low values are false positives. If they are false positives, this sample size will provide the opportunity of determining whether this phenomenon is unique to the CGMS or whether it also occurs with the GW biographer.

These results will then be used to determine the objectives for subsequent studies and will provide variance estimates to be used in sample size determinations.

An estimate of the precision possible with 10 and 20 subjects can be obtained from data available for sensor use in diabetic subjects. The table below shows the 95% confidence interval half-width for a sample size of 10 subject based on standard deviations estimated from a prior accuracy study of diabetic subjects.

	Mean*	Standard Deviation*	Sample Size	
			20	10
			Half-width of 95% CI	
Outcome Measure Computed for Each Subject				
Proportion with deviation $\leq 20\%$.61	.18	.08	.11
Proportion with deviation $\leq 30\%$.77	.15	.07	.09
Mean Relative Absolute Deviation	.21	.09	.04	.06
Mean Absolute Deviation	30.6	11.1	4.9	6.9
Mean Relative Deviation	.08	.14	.06	.09
Mean Deviation	5.0	21.5	9.4	13.4

*estimate from dataset of diabetic subjects

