7.2 Statistical Analysis

Analyses will primarily be exploratory.

To assess the accuracy of low blood glucose values obtained with the sensor, time periods of sensor values below 60 mg/dl will be identified and sensor values will be compared with gold standard values obtained during the same time period.

- To assess overall accuracy, analyses will be conducted similar to those planned for the diabetic subject protocol. For analysis, the gold standard blood glucose values will be paired with the appropriate corresponding sensor values, and the difference between values will be computed. Accuracy will be evaluated by computing the mean and standard deviation for the following parameters and then constructing 95% confidence intervals around the mean: difference, absolute difference, relative difference and absolute relative difference.

Each accuracy measure will be computed on a subject level and then the mean, standard deviation, and 95% confidence interval around the mean will be computed across subjects.

The sensor failure rate will be determined. The frequency of missed sensor readings and the reasons will be tabulated. Adverse events will be tabulated and their incidence estimated.

After the first 10 subjects, the data will be assessed to determine whether any subjects have experienced periods of nocturnal hypoglycemia with the sensors and, if yes, whether the low values were corroborated on the gold standard measurements. If false low glucose values with the sensor occur, then consideration will be given to modifications in the protocol or data collection to try to determine why this is occurring.

References

1. Tamada, J.A., et al., Noninvasive glucose monitoring: comprehensive clinical results. *JAMA*, 1999. 282(19): p. 1839-44.
2. Pitzer, K.R., et al., Detection of hypoglycemia with the GlucoWatch Biographer. *Diabetes Care*, 2001. 24(5): p. 881-5.
3. Tierney, M.J., et al., The GlucoWatch Biographer: a frequent, automatic and noninvasive glucose monitor. *Ann Med*, 2000. 32: p. 632-41.
4. Garg, S.K., et al., Correlation of fingerstick blood glucose measurements with GlucoWatch Biographer glucose results in young subjects with type 1 diabetes. *Diabetes Care*, 1999. 22(10): p. 1708-14.
5. Eastman, R.C., et al., Use of the GlucoWatch Biographer in children and adolescents with diabetes. *Diabetes Care*, 2001. submitted for publication.

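### The 95% CI half-widths in the section 7.1 precision table use the normal multiplier 1.96 as if the SD were known, so they are somewhat too narrow for intervals whose SD is estimated from 10 or 20 subjects

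*Protocol*

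**What the plan says.** Section 7.1 of the protocol gives the reason for the sample size first: "The sample size of 20 normal subjects was selected to provide preliminary data on the accuracy of the sensors in normal children". It adds that several of the 20 children are expected to show long periods of low CGMS values, which can then be checked against the gold standard.

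It then turns to precision: "An estimate of the precision possible with 10 and 20 subjects can be obtained from data available for sensor use in diabetic subjects". The table that follows has one row per accuracy measure, giving the mean, the SD and the half-width at n=20 and then at n=10. Two rows carry enough digits to show how the half-widths were computed: "Mean Absolute Deviation 30.6 11.1 4.9 6.9" and "Mean Deviation 5.0 21.5 9.4 13.4". No multiplier is named, and nothing says that the SD is taken as known. The sentence introducing the table describes its entries as the "95% confidence interval half-width for a sample size of 10 subject based on standard deviations estimated from a prior accuracy study" of diabetic subjects; it mentions only n=10, although both columns are printed.

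Section 7.2 describes the analysis that the table anticipates. Each accuracy measure is computed per subject, and then "the mean, standard deviation, and 95% confidence interval around the mean will be computed across subjects". It describes the analyses as mainly exploratory.

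**The concern.** A multiplier of 1.96 is exact for a mean only when the SD is known. Under section 7.2 the SD comes from the same 10 or 20 subjects as the mean. Section 7.1 itself says that this study will supply variance estimates for later work, so the diabetic-subject SD is not being taken as known for healthy children. At these sample sizes the t multiplier is visibly larger than 1.96. A reader who takes the table as the width of the intervals to be reported is therefore given figures that err in the favourable direction. What is at stake is the accuracy of the stated precision, chiefly in the n=10 column.

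**Working it through.** **Inputs.** The SDs (.18, .15, .09, 11.1, .14, 21.5) and the printed half-widths come from the section 7.1 table. The interval is two-sided 95%. The two-sided 5% multipliers are z = 1.960, t(19 df) = 2.093 and t(9 df) = 2.262.

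**Step 1: reproduce the printed figures.** Half-width = 1.960 × SD/√n. For mean absolute deviation:

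- n=20: 1.960 × 11.1/√20 = 4.86, printed 4.9
- n=10: 1.960 × 11.1/√10 = 6.88, printed 6.9

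**Step 2: compute the t-based figures.** Half-width = t(n−1) × SD/√n. For the same row:

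- n=20: 2.093 × 11.1/√20 = 5.20
- n=10: 2.262 × 11.1/√10 = 7.94

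All rows:

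| Measure | SD | n=20 printed | z | t | n=10 printed | z | t |
|---|---|---|---|---|---|---|---|
| Proportion ≤20% | .18 | .08 | .079 | .084 | .11 | .112 | .129 |
| Proportion ≤30% | .15 | .07 | .066 | .070 | .09 | .093 | .107 |
| Mean relative absolute deviation | .09 | .04 | .039 | .042 | .06 | .056 | .064 |
| Mean absolute deviation | 11.1 | 4.9 | 4.86 | 5.20 | 6.9 | 6.88 | 7.94 |
| Mean relative deviation | .14 | .06 | .061 | .065 | .09 | .087 | .100 |
| Mean deviation | 21.5 | 9.4 | 9.42 | 10.06 | 13.4 | 13.33 | 15.38 |

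The z formula gives 11 of the 12 printed values directly. The twelfth (13.33 against 13.4) fits once rounding of the SD is allowed: an unrounded SD of about 21.54 to 21.55 gives both 9.4 and 13.4.

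**Step 3: confirm the multiplier.** Solve printed half-width × √n/SD for the two rows with most digits, allowing for rounding of both the SD and the half-width:

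- Mean absolute deviation: 1.945–2.003 (n=20) and 1.943–1.989 (n=10)
- Mean deviation: 1.940–1.970 (n=20) and 1.959–1.983 (n=10)

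All four ranges contain 1.96, and none reaches 2.093 or 2.262. A multiplier of exactly 2 gives 4.96, 7.02, 9.62 and 13.60, which do not round to the printed values.

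**Step 4: size of the difference.**

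- If the observed SD equals the tabulated SD, the ratio of t to z is 2.262/1.960 = 1.154 at n=10 and 2.093/1.960 = 1.068 at n=20.
- If the tabulated SD is the true SD and the data are normal, the sample SD averages c4 × SD, with c4 = .973 at n=10 and .987 at n=20. The expected excess is then 1.154 × .973 = 1.12 and 1.068 × .987 = 1.05.

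**Step 5: which cells change at the printed precision.**

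- n=10, five of six: .11 to .13, .09 to .11, 6.9 to 7.9, .09 to .10, 13.4 to 15.4.
- n=20, three of six: 4.9 to 5.2, .06 to .07, 9.4 to 10.1. The move from .06 to .07 is .061 to .065 before rounding, so much of it is rounding.

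**The case against.** The strongest reply is that nothing depends on these figures. The sample size rests first on a qualitative argument, the table follows as an indication of achievable precision, and no target width or decision rule uses it. The SDs come from diabetic subjects, which section 7.1 discloses. A sample SD also has a relative standard error of 1/√(2(n−1)) under normality, about 24% at n=10 and 16% at n=20. Against that uncertainty a 7% change in the multiplier is small, and at the planned n=20 three of the six rows do not change. All of this stands. It limits the consequence but does not make the printed values right for the planned interval.

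Four stronger readings are tempting, and the documents do not support them:

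- **That n=20 loses its justification.** Section 7.1 gives a separate reason for n=20 and sets no precision target, so no target is missed.
- **That the look after 10 subjects is affected.** Sections 1.2 and 7.2 describe that look as a check on whether sensor lows occurred and were corroborated, and whether the protocol should be modified. No accuracy interval is planned there.
- **That the reported intervals would cover only about 92% (n=10) or 93.5% (n=20).** Those figures are P(|t| < 1.96) with 9 and 19 degrees of freedom. They apply to an interval of mean ± 1.96 × sample SD/√n, which section 7.2 does not prescribe. An interval of the fixed printed width, with the tabulated SD true, would cover 95% apart from rounding.
- **That section 7.2 is wrong.** It names no multiplier and misstates nothing. The choice of distribution can be left to the statistical analysis plan.

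**Conclusion.** The point holds as a minor correction. The section 7.1 half-widths were computed with 1.96 and an SD treated as known, without saying so. The multiplier is inferred rather than stated, but the rows with most digits leave little doubt. For the interval described in section 7.2, the t-based widths are about 15% larger at n=10 and 7% larger at n=20 if the observed SD equals the planning SD. They are about 12% and 5% larger in expectation if the planning SD is the true SD. Both pairs assume roughly normal subject-level measures, and neither addresses whether SDs from diabetic subjects carry over to healthy children. The error makes precision look better than it is, mainly at n=10. It does not call into question the sample size, the look after 10 subjects or any planned analysis.

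**What to change.** Replace the half-widths in the section 7.1 table with the t-based values, in row order:

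- n=20: .08, .07, .04, 5.2, .07, 10.1
- n=10: .13, .11, .06, 7.9, .10, 15.4

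If the unrounded SDs are at hand, compute from those, since the last digit of some cells depends on SD rounding. The sentence introducing the table can name both sample sizes in the same edit. The cost is eight changed cells and a slightly less favourable statement of precision. No subjects or procedures are added, and section 7.2 stays as written.
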